6.3.2.2. Clinical Status Ordinal Scale

Additional derivation of clinical status will be performed. If subject dies then their clinical status will be recorded as 8-Death from date of death to Day 60 inclusive, this will override any collected clinical status.

Otherwise if clinical status is missing and the assessment day is prior to last contact with participant, then the following rules will apply:

Category	Rule
8 - DEATH	Date of death <= date of assessment
7 - HOSPITALIZED, MECHANICAL VENTILATION+ADDITIONAL ORGAN SUPPORT	Ventilation = "INVASIVE MECHANICAL VENTILATION" and additional support includes: "EXTRACORPOREAL MEMBRANE OXYGENATION" "RENAL REPLACEMENT THERAPY (RRT)/DIALYSIS" "INOTROPES/VASOPRESSORS"
6 - HOSPITALIZED, INTUBATION AND MECHANICAL VENTILATION	Ventilation = "INVASIVE MECHANICAL VENTILATION" and does not meet the classification for additional organ support

Category	Rule
5 - HOSPITALIZED, HIGH-FLOW OXYGEN(\geq 15L/MIN), CPAP, BIPAP, NIV	Ventilation is: "NON-INVASIVE MECHANICAL VENTILATION" or "HIGH-FLOW OXYGEN THERAPY (\geq 15 L/MIN)"
4 - HOSPITALIZED, LOW-FLOW OXYGEN BY MASK OR NASAL PRONGS	Ventilation = "LOW-FLOW OXYGEN THERAPY" and date of discharge to non-hospitalized residence is missing or greater than date of assessment
3 - HOSPITALIZED, NO OXYGEN THERAPY	Date of assessment < date of discharge to non-hospitalized residence and Date of assessment > date of last oxygen usage
2 - NON-HOSPITALIZED, LIMITATION OF ACTIVITY	Date of assessment > date of discharge to non-hospitalized residence and participant has not been re-hospitalized and date of assessment > date of last oxygen usage and does not meet the classification for group 1.
1 - NON-HOSPITALIZED, NO LIMITATION OF ACTIVITY	Date of assessment > date of discharge to non-hospitalized residence and participant has not been re-hospitalized and date of assessment > date of last oxygen usage and last and subsequent recorded assessment is "1 - NON-HOSPITALIZED, NO LIMITATION OF ACTIVITY".

All non-Death derived values will be flagged in the dataset.

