4.2. Primary Endpoint(s) Analyses

4.2.1. Definition of Endpoint(s)

Participants are free of respiratory failure if they are in category 1, 2, 3 or 4 from the GlaxoSmithKline (GSK) modified ordinal scale adapted from World Health Organization (WHO, 2020) scale 2020 (See [Table 2](#) - Clinical Status using Ordinal Scale). Missing data prior to study withdrawal will be derived using ventilation data as described in [Section 6.3.2](#).

Participants will meet the endpoint if they are alive and free of respiratory failure at Day 28. As participants may be discharged from the investigator site prior to Day 28, analysis windows will be used to define the endpoint as described in [Section 6.3.1](#).

Table 2 Clinical Status using Ordinal Scale**Ordinal Scale (GSK modified version, adapted from WHO, 2020 version)**

CCCCI - This section contained Clinical Outcome Assessment data collection questionnaires or indices, which are protected by third party copyright laws and therefore have been excluded.

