4.4.1.10. Oxygen Use Following Discharge to Non-hospitalized Residence

The number of participants will be presented for the following categories:

- Not discharged to non-hospitalized residence or death
- Discharged to non-hospitalized residence and used oxygen post-discharge

- Discharged to non-hospitalized residence and did not use oxygen post-discharge.

In addition, for participants discharged to a non-hospitalized residence and for oxygen usage post-discharge, the number of days on oxygen will be summarized for each participant for the following:

- 1-< 7 days
- 7- <14 days
- \geq 14 days.

Summary statistics for the number of days of oxygen use, including mean, median (IQR), min and max will also be provided.

4.4.1.11. Time to Improvement of at Least 2 Categories Relative to Baseline in Clinical Status up to Day 60

Time from dosing (days) to final improvement of at least 2 categories relative to baseline in clinical status (see [Table 2](#)) up to (and including) Day 60. Evaluated for all participants with clinical status greater than 2 at baseline.

Note: if a participant has an improvement of at least 2 categories relative to baseline but then progresses back to a less than 2 category improvement the participant has not had their final improvement of at least 2 categories.

This endpoint will use a composite approach such that if the event has not occurred prior to the intercurrent event of death (on or prior to Day 60), then time will be censored at the end of follow-up (Day 60).

4.4.1.12. Number of Days in Each Category of Clinical Status up to Day 60

For each participant, the number of days in each clinical status (see [Table 2](#)) or missing will be calculated up to (and including) Day 60.

The median number of days in each category will be presented overall. a participant's final outcome (Alive vs Dead or Withdrawn)

4.4.1.13. Change in COVID-19 Signs and Symptoms up to Day 60

Participants change in COVID-19 signs and symptoms at Day 4, 7, 14, 28, 42 and 60 relative to baseline will be analysed. Participants will be absent of a symptom if they had a symptom at baseline and the symptom was not present at the timepoint of interest. This endpoint will use a composite approach for death or initiation of invasive mechanical ventilation, such that participants who die prior to or are using invasive mechanical ventilation on the day of interest (and so cannot have symptoms recorded), will be considered to still have the symptom.

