6.3.2. Derived and Transformed Efficacy Data

6.3.2.1. Ventilation Status

Ventilation status as shown below, will be derived for Days 1-60 based on the log-based collection (start and end dates/time).

Code	Decode
1	None
2	Low flow oxygen therapy
3	High-flow oxygen therapy (>= 15 L/min)
4	Non-invasive mechanical ventilation
5	Invasive mechanical ventilation
6	Death
99	Other

Ventilation status at baseline is defined as the ventilation status at the time of dosing, if no ventilation is recorded then the last ventilation use will be assigned to baseline. If multiple ventilation types are being used at the start of baseline the worst case is assumed.

For post-baseline the worst-case ventilation on a day will be used, Other will only be considered worst-case if no other ventilation is recorded.

Ventilation statuses with missing end-dates will be assumed ongoing.

Ventilation status will only be missing after last contact for subjects who have withdrawn from the trial, such that participants with no open ventilation logs will be assumed to have Ventilation=None.

Other will not be included in figures

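### Part 2 SAP 6.3.2.2: read literally, the fill-in rules for categories 1 to 3 let later oxygen use (or, for 1 and 2, later re-hospitalization) leave an earlier missing day uncategorised

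*SAP*

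**What the plan says.** Section 6.3.2.2 of the Part 2 SAP fills gaps in the ordinal scale. Apart from death, which overrides everything, the rules act only on gaps: "Otherwise if clinical status is missing and the assessment day is prior to last contact with participant, then the following rules will apply".

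- Categories 4 to 7 start from the ventilation status. Category 4 also looks at whether discharge home is missing or later than the assessment date.
- Categories 1, 2 and 3 each require "Date of assessment > date of last oxygen usage".
- Categories 1 and 2 add that the "participant has not been re-hospitalized". Category 3 has no such clause.
- Category 1 also uses the recorded assessments on either side of the gap.

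The day's oxygen status is available separately. Section 6.3.2.1 states: "Ventilation status as shown below, will be derived for Days 1-60 based on the log-based collection". A day with no open log counts as Ventilation = None, and ventilation is missing only after last contact in withdrawn participants. Section 4.2.1 says of the primary endpoint: "Missing data prior to study withdrawal will be derived using ventilation data". Section 4.4.1.12 counts each participant's days in each clinical status "or missing will be calculated up to (and including) Day 60".

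**The concern.** The last date of oxygen use is a single date per participant. Unless it is cut off at the assessment day, it carries information from the future. Two participants with the same status on a given day are then treated differently according to what happens to them weeks later: one is derived as category 1, 2 or 3, and the other is left missing.

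At an analysis visit, a status left missing is imputed under missing at random (4.1.5), using preceding visits only (6.2.1). The relapse that created the gap therefore cannot inform the imputation. The same participants also count as missing in the tipping-point analysis (4.2.3.1).

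In the days-in-each-category summary, relapsers lose days at home to the missing bin. Section 4.8 says the added exploratory analyses were requested to quantify resource use, specifically around oxygen and glucocorticoids, and relapsers are an important group for that purpose.

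**Working it through.** The plan states no figure on this point, so the check is of the rule itself.

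**1. Logic.** Let d be a day with missing status, before last contact, with the participant alive and Ventilation = None. Suppose oxygen is next used on day r > d. The last oxygen date L is then at least r, so d > L is false and categories 1, 2 and 3 all fail. Ventilation = None, so categories 4 to 7 fail. The participant is alive, so category 8 fails. No category is assigned. Without the relapse, L < d and the day is category 1, 2 or 3 (the discharge day itself aside).

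**2. Worked example (assumed history).** Discharged home on Day 12 off oxygen; status 2 recorded at the Day 14, 28 and 42 calls; re-hospitalized on oxygen Days 50-55.
- Days at home off oxygen: Days 13 to 49, 49 − 13 + 1 = 37.
- Days with a recorded status, which stand: 3.
- Days left missing under the literal rule: 37 − 3 = 34, or 34/37 = 92%.
- Without the Day 50 relapse, all 37 are classified.

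**3. Other assumed histories.** Oxygen Days 1-10 and discharge home on Day 14 unless stated. To isolate the rule, status is treated as missing on every day. The counts are off-oxygen days in Days 1-60 with no category.

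| History | Literal | As of the day | Difference |
|---|---|---|---|
| No relapse | 1 | 1 | 0 |
| Re-hospitalized on oxygen Days 35-40 | 44 | 21 | 23 |
| Home oxygen Days 35-40, not re-hospitalized | 24 | 1 | 23 |
| Re-hospitalized Day 35, no oxygen | 47 | 27 | 20 |
| Oxygen again in hospital Days 20-24, home Day 30 | 10 | 1 | 9 |

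The days that remain under the as-of-day reading are the discharge day itself, which fits none of categories 1 to 3, and in the two re-hospitalization rows the off-oxygen days from re-hospitalization onward (20 and 26 days). In rows two to four, Day 28 has no category literally but is category 1 or 2 as of the day. In the fourth row, Days 11-13 keep category 3 under both readings, because that rule has no re-hospitalization clause.

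**4. Reach for the primary endpoint.** The protocol's Part 2 schedule records the scale daily until discharge (or Day 28 if still in hospital), then at follow-up contacts. The SAP window for Day 28 is Days 26-30 (6.3.1). The rule matters only if no status is recorded in that window, a later contact exists, and oxygen use or re-hospitalization follows. Anyone alive with Ventilation = None falls in categories 1 to 3 and is a responder, since response is categories 1 to 4. The literal rule sends that person to imputation. The same reasoning applies to a missed Day 42 contact.

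**5. Day 60.** A look-ahead effect would need a relapse after the assessment day, reported at a later contact. Planned follow-up ends at Day 60 ± 2 days, and a status recorded anywhere in Days 53-67 is slotted to Day 60.

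**The case against.** The strongest reply is that the rules were meant to be read as of the assessment day. Each is evaluated at a date of assessment, the re-hospitalization clause reads naturally as meaning by that date, and where later information was wanted (category 1) the SAP says so. Section 1 also leaves further data-handling detail to the Output and Programming Specification, which is not available here. This stands as a possibility. But the same table ties death, and discharge in category 4, explicitly to the assessment date, and does not do so for these two clauses. Two programmers could code them differently.

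Other replies also have weight. After discharge, Ventilation = None is assumed from the absence of an open log, but the SAP makes that assumption for relapsers and non-relapsers alike. Withholding categories 1 and 2 from re-hospitalized participants could be deliberate caution; that could explain days after readmission, not days before it. The days-in-category summary is exploratory, is presented as medians and has an explicit missing count. Oxygen-free days (4.4.1.6) use ventilation records directly and are unaffected.

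A reader might go further than the documents allow in four ways:
- That a relapse strips recorded categories: the rules act only on missing statuses.
- That the re-hospitalization clause covers category 3: it does not.
- That Day 60 status is at risk: step 5 of the working shows essentially no route.
- That the primary treatment effect is materially biased: affected participants are imputed rather than counted as failures, should be few, and nothing shows a difference between arms.

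**Conclusion.** The point holds as a defect in a stated rule. Taken literally, section 6.3.2.2 leaves uncategorised a missing day that sections 4.2.1 and 6.3.2.1 together would resolve, solely because of a later event. Whether the look-ahead was intended cannot be settled from the documents.

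Its main effect is on the exploratory days-in-each-category summary, where many post-discharge days have a status only through this derivation. The 34 of 37 days illustrates one assumed history; it does not estimate how often this happens. The effect on Day 28, and likewise Day 42, is confined to a missed contact followed by a relapse, and should be small. The documents give no relapse or missed-contact rates, so no overall size can be calculated. The correction is worth making because the rule lets later outcomes decide whether earlier status is used.

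**What to change.** For categories 1, 2 and 3, replace the last-oxygen-date condition with Ventilation = None on the assessment date. For categories 1 and 2, limit the re-hospitalization condition to the participant not having been re-hospitalized as of the assessment date, using re-hospitalization dates where they are recorded. If the as-of-day reading was always intended, state it in the rule before unblinding.

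The oxygen part needs only SAP wording and derivation code, because ventilation is already derived for Days 1-60; sample size is unaffected. The re-hospitalization part depends on readmission dates being collected. The documents do not confirm this: protocol section 7.2.7 covers baseline and discharge location, and the Part 1 SAP (Table 2) says the eCRF guidelines take re-hospitalization to refer to the investigator site. The sponsor should check which dates exist. For the primary endpoint, the ventilation condition and survival are enough to identify a responder, wherever the participant is staying.

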6.3.2.3. Fraction of Inspired Oxygen (FiO₂)

FiO₂ may be derived from oxygen flow rate. For participants not yet discharged from investigator site, if a participant has missing FiO₂ who have reported any of the following ventilation procedures on that day:

- HIGH-FLOW OXYGEN THERAPY
- LOW-FLOW OXYGEN THERAPY

Then FiO₂ will be derived from Oxygen flow rate using the formula:

$$FiO_2 = \min(24 + (\text{Oxygen flow rate} - 1) * 4, 100)$$

This is consistent with the reference that for 1 L/min (Oxygen flow rate) the FiO₂ is 24% then thereafter the FiO₂ increases by 4% for every 1 L/min increase of oxygen flow rate, (or 2% for every 0.5 L/min) up to a maximum of 100%.

FiO₂ will not be derived if participants are using non-invasive or invasive mechanical ventilation

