7.2.3. Concentration of inspired oxygen (FiO₂)

Concentration of inspired oxygen (FiO₂) and/or oxygen flow rate (L/min) should be measured at the timepoints defined in the SoA (Section 1.3 and Section 1.4).

Part 2: FiO₂ and/or oxygen flow rate should be measured once daily in the morning (up to discharge) at approximately the same time as the Ordinal Scale categorisation.

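### When only flow is recorded on high-flow oxygen, the SAP's FiO₂ formula can return only 80–100%, which can distort the exploratory change from baseline in FiO₂

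*SAP*

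**What the plan says.** Part 2 SAP Section 6.3.2.3 sets derived FiO₂ to min(24 + (flow − 1) × 4, 100). It explains the rule as "for 1 L/min (Oxygen flow rate) the FiO₂ is 24% then thereafter the FiO₂ increases by 4" percentage points "for every 1 L/min increase of oxygen flow rate, (or 2% for every 0.5 L/min) up to a maximum of 100" per cent.

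The rule runs before discharge from the investigator site, and only "if a participant has missing FiO₂ who have reported any of the following ventilation procedures on that day". Two procedures are listed: "HIGH-FLOW OXYGEN THERAPY" and "LOW-FLOW OXYGEN THERAPY". Under non-invasive or invasive mechanical ventilation FiO₂ is not derived.

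Section 6.3.2.1 codes the high-flow mode as "High-flow oxygen therapy (>= 15 L/min").

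Section 4.4.1.9 uses the derivation for change from baseline in FiO₂ up to Day 28 when flow is recorded and FiO₂ is not. The endpoint is summarised as a fraction, on observed data and by trimmed means (Section 4.4.2.4).

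Protocol Section 7.2.3 says that in Part 2 FiO₂ and/or "oxygen flow rate should be measured once daily in the morning". A day with flow alone is therefore allowed.

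**The concern.** One straight line is used for both oxygen modes. The high-flow mode starts at 15 L/min and the line reaches its cap at 20 L/min. Over most of the high-flow range the derived value therefore comes from the cap and says nothing about the flow recorded that day.

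High-flow oxygen at 15 L/min or more is an entry route (Protocol Section 5.2). Category 6 is targeted at no more than about 40% of Part 2 (Protocol Section 4.1.2.2), so about 60% or more should enter in category 5. That category includes high-flow oxygen but also non-invasive ventilation, where nothing is derived. A flow-only high-flow value at baseline would carry into every later change for that participant.

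Section 4.8 of the SAP says the added exploratory endpoints were requested to quantify resource use, oxygen in particular. A value fixed at 100% serves that purpose poorly. Nothing planned would show how much of the result is formula output. Section 6.3.2.2 flags derived clinical-status values, but 6.3.2.3 has no such flag, and the exploratory sensitivity analyses in Section 4.4.3 concern time-to-event endpoints only.

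**Working it through.** **Inputs.** Formula, cap, trigger and listed modes: SAP 6.3.2.3. High-flow threshold of 15 L/min: SAP 6.3.2.1. Delivered FiO₂ on high-flow oxygen and the share of flow-only records: not in the documents.

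**Step 1: reproduce the SAP's own rule.** 1 L/min gives 24 + 0 = 24%. 1.5 L/min gives 24 + 0.5 × 4 = 26%. 2 L/min gives 24 + 1 × 4 = 28%. Formula and prose agree.

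**Step 2: where the cap binds.** 24 + (flow − 1) × 4 = 100 gives flow = 76/4 + 1 = 20 L/min.

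| Flow (L/min) | Without cap (%) | Derived FiO₂ (%) |
|---|---|---|
| 4 | 36 | 36 |
| 15 | 80 | 80 |
| 18 | 92 | 92 |
| 20 | 100 | 100 |
| 30 | 140 | 100 |
| 40 | 180 | 100 |
| 60 | 260 | 100 |

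Every derived high-flow value lies in 80–100%. From 20 L/min upward it is always 100%.

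**Step 3: changes between derived days.** Between two derived high-flow days the change can lie only between −20 and +20 points. If both flows are 20 L/min or more it is 0. From 20 L/min or more down to 4 L/min it is 36 − 100 = −64 points, or −0.64 as a fraction.

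**Step 4: error against delivered FiO₂.** This needs an assumption, so a range is shown (derived minus delivered, in percentage points).

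| Assumed delivered FiO₂ (%) | 40 | 50 | 60 | 80 | 100 |
|---|---|---|---|---|---|
| Error at 15 L/min (derived 80%) | +40 | +30 | +20 | 0 | −20 |
| Error at 20 L/min or more (derived 100%) | +60 | +50 | +40 | +20 | 0 |

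Take the step-down in Step 3 and accept 36% for the second day. A delivered baseline of 40–100% would then mean a real change between 36 − 40 = −4 and 36 − 100 = −64 points. The derived change is −64 in every case. If a participant has 50% recorded on one day and only a flow of 20 L/min or more on the next, with no change in delivery, the data show a rise of 100 − 50 = 50 points.

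**Step 5: baseline.** SAP Section 4.1.2 leaves a missing baseline missing unless otherwise stated. I read 6.3.2.3, which makes no exception for pre-dose days, as such a statement. If the sponsor reads it otherwise, derived values enter only at follow-up.

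**The case against.** The strongest reply is that little rests on this. The endpoint is exploratory, may be analysed at the final analysis only (Section 4.4), is outside the hierarchy in Section 2.1, and is summarised without a comparison model. The rule is the same in both arms of a double-blind, centrally randomised trial, and no difference between arms is shown. All of that stands.

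Four stronger readings are tempting, and the documents support none of them.

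- *All high-flow FiO₂ values are forced to 80–100%.* They are not. The formula runs only where FiO₂ is missing and flow is present.
- *The FiO₂ endpoint is wrong.* This is not shown. Permission to record flow alone does not tell us how often sites do so, and the error can be nil.
- *Flow and oxygen fraction are set separately on high-flow devices, so the rule is invalid there.* The documents name no device, define the mode by flow, and rest the rule on a reference they do not identify. The arithmetic above does not need this premise.
- *The formula gives 20% at 0 L/min and needs a floor of 21%.* The rule runs only on days with low-flow or high-flow oxygen reported. Independence from oxygen with missing FiO₂ is handled separately in Section 4.4.1.9, so 20% is not a realistic output and no floor is needed.

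The reply also has force against the fix: removing derived high-flow values takes out sicker days while low-flow days after step-down stay in. That is a reason to show both versions.

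**Conclusion.** The concern holds for flow-only records on high-flow oxygen. For those records the derived FiO₂ must be 80–100%, and exactly 100% from 20 L/min. This follows from the SAP's formula and its 15 L/min threshold, with no outside premise. Change from baseline in FiO₂ can be materially distorted where such values enter.

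The overall size cannot be given. Per record, with an assumed delivered FiO₂ of 40–100%, the error runs from +60 to 0 points at 20 L/min or more, and from +40 to −20 points at 15 L/min. The number of affected records is unknown, and no direction of bias between arms is established. The primary endpoint and the secondary testing hierarchy do not use derived FiO₂ and are unaffected.

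**What to change.** In Section 6.3.2.3:

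- Limit the flow formula to "LOW-FLOW OXYGEN THERAPY" and do not derive FiO₂ on high-flow oxygen, as is already the rule for non-invasive and invasive ventilation.
- Flag every derived FiO₂ value, and report the number of derived values by arm and by oxygen mode.
- Give the summary that includes formula-derived high-flow values as a sensitivity analysis.
- State whether the derivation applies to the baseline value.

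The work is one programming condition, a flag, one repeated summary and a few lines of SAP text. The real cost is lost data. Flow-only high-flow values become missing. After baseline, Section 4.4.2.4 treats them as missing at random and outside the trimmed sample. At baseline, Section 4.1.2 falls back on the latest earlier non-missing pre-dose value; where there is none, the participant has no change score. These are the sicker days, so neither version should be shown alone.
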